4. STUDY OBJECTIVES

Aim: To evaluate the feasibility/acceptability of an RCT to assess the clinical and cost effectiveness of our co-adapted intervention.

Objectives:

- To train 4-6 facilitators to deliver our co-adapted intervention.
- To recruit 40 young people (four groups of ten, across four sites) to participate in a trial to evaluate the feasibility of a cluster-randomised controlled trial to determine the clinical and cost-effectiveness of our intervention by quantifying participant recruitment, retention and 3-month follow up rates.
- To determine intervention acceptability and identify from multiple stakeholder perspectives the barriers and facilitators to implementation.

Version: 2 Date: 11/7/2022 UREC ID: 2022-14361-24300

- To examine the applicability (content-validity) and acceptability (full and partial completion rates, sensitivity to change) of proposed trial outcome measures and the need for additional CYP prioritised outcomes.
- To collect outcome data to inform parameters for a fully-powered trial, including the identification and standard deviation of the proposed outcomes measure needed to estimate trial sample size.
- To co-produce with stakeholders a protocol for definitive evaluation of our intervention.

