5. STUDY DESIGN AND PROTOCOL

The MRC recommends feasibility testing to ensure new interventions can be implemented prior to undertaking definitive evaluations through fully powered randomised controlled trials [44].

Design: A multi-site, cluster-randomised feasibility trial with nested process evaluation.

Target population: 40 CYP aged 12-14, attending school and community settings (study sites) in Greater Manchester. This age range was chosen following PPI consultation as it corresponds to key stage 3 in the UK educational system, is pre-exam curriculum stage and is relevant in terms of mental illness prevention as the peak period of onset is in the mid to late teens. Parents/guardians (n=6-10), professionals (n=6-10) and facilitators (n=4-6) will also participate alongside CYP participants in the nested process evaluation.

Participants must have capacity to consent (checked at each assessment point) and be able to read and write in English to engage with study materials. Translation of materials is not possible in the current study but will be prioritised in a future study should our intervention show promise. CYP participants need to have access to a smartphone/tablet to use the intervention.

Setting: Education and community settings in Greater Manchester.

Sample size: Our feasibility trial will not formally test intervention effect so a formal power calculation is not appropriate. Instead, sample size has been selected to allow us to assess key feasibility outcomes (recruitment, retention, intervention uptake) and to allow sufficient replications of the study protocol to highlight barriers to completion in the main trial. The sample size will also allow us to estimate differences in means for intervention outcomes to within 0.25 standard deviations.

Recruitment: Four sites (schools/ community venues) will be recruited to the study. All eligible CYP in participating sites will be invited to take part. Educational professionals and community leaders (facilitators) will issue study information to potential participants and obtain CYP assent and parental consent and contact information and collect CYP baseline measures. Direct invitations and information sheets will be available at participating sites so that interested participants can enquire about the study directly.

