Randomisation: In this study, an equal number of clusters (two per arm) will be allocated to the intervention and control arms. This will be achieved by using a blocked randomisation list. The study statistician will produce the randomisation list. A cluster will not be allocated until the full set of 10 participants have been recruited at that cluster, to prevent allocation bias. The allocation

Version: 2 Date: 11/7/2022 UREC ID: 2022-14361-24300

sequence will not be revealed to the other study investigators. Outcome data will predominantly be self-report.

Intervention: Our intervention combines an interactive individual game in conjunction with prepost facilitated group discussions. Our candidate intervention will be co-adapted in phase 1 and additional content and materials co-produced with a range of stakeholders including CYP, parents, professionals and community members.

Group-delivery is a low-cost delivery model which can derive additional benefits through peer-topeer support. Systematic review and meta-analysis [49-50] suggests that engaging students in activities such as games, simulations and group work is more effective than relying solely on didactic methods. We will align the structure of our intervention with current evidence [51-53] supporting the effectiveness of short-term programmes for mental health education and mental health first-aid. Frequency, duration and content of the intervention will be recorded by facilitators and reviewed in phase 2 facilitator and CYP interviews to explore whether treatment was delivered as intended.

Minimum levels of intervention require engagement in each of the chapters of the intervention for a minimum of 1 h each and participation in a facilitated group session before and after the intervention (minimum 5-6 hours in total).

The intervention will provide a range of techniques to improve mental health literacy and promote self-management, e.g. cognitive reframing, distraction and/or the substitution of more adaptive behaviours. Intervention content will be standardised via a manual. Intervention facilitators health and community workers will be trained by a multidisciplinary team, comprising co-applicants [name], [name] and a PPI representative.

Fidelity: Frequency, amount and content of the intervention will be recorded by the facilitators and reviewed in CYP interviews to explore whether treatment is delivered as intended.

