We will undertake exploratory comparisons of intervention outcomes on an intention-to-treat basis, recognising that these analyses will be underpowered. These will focus on plausible ranges for effect sizes as indicated by 95% confidence intervals, and will be analysed with adjustment for the corresponding baseline measure of the outcome, in order to improve precision. We will attempt to control for clustering in this analysis by including a random intercept in a mixed model, although the small sample size may prove prohibitive. If this analysis can not be realised, we will adjust for site as a fixed effect. We will also present an adjusted mean difference (95% CI) based on ANCOVA (adjusted for corresponding baseline value of the outcome, with no adjustment for site).

Feasibility success criteria: See success criteria outlined below:

Progression criterion: Willingness of participants to be randomised

- Red: Recruit < 60% of required sample.
- Amber: Recruit 60-80% of required sample.
- Green: Recruitment > 80%.

Progression criterion: Retention in intervention arm

Participants will be considered retained in the intervention arm if they are available for assessment at 3 month follow-up.

- Red: Retain < 60% of participants in the intervention arm at 3-month follow-up
- Amber: Retain 60-80% of participants in the intervention arm at 3-month follow-up
- Green: Retain > 80% of participants in the intervention arm at 3-month follow-up.

Progression criteria: Uptake of intervention

Participants will be considered to have suitably engaged with the intervention if they take part in each of the chapters of the intervention for a minimum of 1 h each and participate in a facilitated group session before and after the intervention (minimum 5-6 hours in total).

Version: 2 Date: 11/7/2022 UREC ID: 2022-14361-24300

- Red: Engage <60% of participants at the requisite level described above.
- Amber: Engage 60-80% of participants at the requisite level described above.
- Green: Engage >80% of participants at the requisite level described above.

Process Evaluation: We will use the MRC process evaluation model [44] to explore the delivery and reach of our intervention and understand barriers/enablers to roll-out.

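### The planned ANCOVA 95% CI ignores the site randomisation and is too narrow, and the fixed-site fallback cannot estimate the intervention effect

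*Protocol*

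**What the plan says.** Protocol section 5 describes the design as "A multi-site, cluster-randomised feasibility trial with nested process evaluation". Under Randomisation, "an equal number of clusters (two per arm) will be allocated to the intervention and control arms". The objective in section 4 gives the sizes: "To recruit 40 young people (four groups of ten, across four sites".

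Under Analysis in section 5, the between-arm comparisons of outcomes are exploratory, by intention to treat, adjusted for baseline, and acknowledged to be underpowered. On their purpose: "These will focus on plausible ranges for effect sizes as indicated by 95% confidence intervals". Three models are named:

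- First choice: "We will attempt to control for clustering in this analysis by including a random intercept in a mixed model". The protocol adds that the small sample may make this impossible.
- Fallback: "If this analysis can not be realised, we will adjust for site as a fixed effect".
- Presented in any case: an "adjusted mean difference (95% CI) based on ANCOVA (adjusted for corresponding baseline value of the outcome, with no adjustment for site".

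The protocol does not say that the last interval is too narrow under clustering, nor which interval is to be read as the plausible range. It states no ICC. Section 9 defers further detail to an SAP, which is not at hand.

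**The concern.** When whole sites are allocated, chance differences between sites are part of the error in the arm comparison. An analysis of individual children that leaves site out does not count that part, so its standard error is too small, and its t multiplier is too small for a contrast between four units. Differences between sites are plausible here: sites may be schools or community venues, and the intervention is delivered to groups by facilitators at each site.

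The other two models do not clearly repair this. The fixed-site fallback has no estimable arm effect. The random-intercept model may return almost the same interval as the ANCOVA when the site variance is estimated as zero.

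At stake is the reading of the exploratory effect ranges. A too-narrow interval can exclude effects that are still plausible, because of nothing more than which sites fell into which arm.

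**Working it through.** **Inputs from the protocol.** Four sites, two per arm, ten children per site, so 20 per arm and 40 in all; two-sided 95% intervals; adjustment for the baseline value.

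**Inputs assumed.** ICC of the baseline-adjusted outcome: 0.02, 0.05, 0.10, 0.20. Correlation of baseline with outcome: 0.5, and 0.6 in a second run.

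**The protocol's own figure.** It states no coverage or ICC to reproduce. Its only precision figure is 0.25 SD (section 5, Sample size). With 20 independent children per arm, SE = √(2/20) = 0.316 SD and the 95% half-width is 1.96 × 0.316 = 0.62 SD, so 0.25 is not reproduced. That is a separate matter and is not used below.

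**Step 1: degrees of freedom.** ANCOVA: 40 children − 3 coefficients = 37 (t = 2.026). Site comparison: 4 sites − 2 arms = 2 (t = 4.303).

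**Step 2: coverage of the ANCOVA interval.** Design effect = 1 + (10 − 1) × ICC. Approximate coverage = 2Φ(1.96/√(design effect)) − 1. Simulation used 20,000 trials per ICC with correlation 0.5.

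**Step 3: how often the site variance is estimated as zero.** For the balanced design this is P(F(2,36) ≤ 1/λ), with λ = 1 + 10 × ICC/(1 − ICC). At ICC 0.05, λ = 1 + 0.5/0.95 = 1.526 and the probability is 0.475.

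| ICC | Design effect | ANCOVA coverage, formula | ANCOVA coverage, simulated | Site variance estimated as zero | Random-intercept coverage, normal multiplier |
|---|---|---|---|---|---|
| 0.02 | 1.18 | 0.929 | 93% | 55% | 94% |
| 0.05 | 1.45 | 0.896 | 90% | 47% | 93% |
| 0.10 | 1.90 | 0.845 | 84% | 37% | 90% |
| 0.20 | 2.80 | 0.759 | 75% | 25% | 86% |

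The second run (2,500 trials per ICC, correlation 0.6) gave ANCOVA coverage of 93.6% at ICC 0.01, 90.5% at 0.05, 84.4% at 0.10 and 75.1% at 0.20. At ICC 0 it gave 95.1%, as it should.

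**Step 4: the fixed-site fallback.** The columns are intercept, arm, baseline and three site indicators: six columns, rank five. Arm is the sum of the indicators of the two intervention sites, so it carries nothing beyond site. Software that drops a column to fit the model would report a contrast between particular sites, not the intervention effect.

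**Step 5: an interval with the right coverage.** Baseline-adjusted site means compared with t on 2 df covered about 95% at every ICC tried (94–95% in the second run). At ICC 0.05 and correlation 0.5 the median half-width is 1.19 SD, against 0.55 SD for the ANCOVA. Check for the ANCOVA: 2.026 × 0.316 × √(1 − 0.25) = 0.55. Check for the site means: 4.303 × √(0.1 × 0.75 × 1.45) × √(ln 2) = 1.18, where √(ln 2) converts the expected variance on 2 df to its median.

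**The case against.** The comparisons are exploratory, called underpowered, and secondary to feasibility outcomes. The ANCOVA comes in addition to a mixed model, and its lack of site adjustment is stated openly. This limits how much the point matters, but does not answer it. Low power warns of wide intervals, whereas the fault is an interval that is too narrow. Saying that site is left out does not tell a reader that the coverage is below 95%.

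Baseline adjustment may absorb part of the site differences. That is correct, and it is why the ICCs above are residual ones. If the residual ICC is 0.01 to 0.02, the loss is only 1 to 2 percentage points.

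Three stronger readings are tempting and are not supported:

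- *That the intervals are to be carried forward as the effect size for the definitive trial.* The protocol does not say so. Section 4 names the standard deviation as the quantity needed for the future sample size.
- *That the progression decision is affected.* The three criteria concern recruitment, retention and engagement, and none uses these intervals.
- *That the random-intercept model is itself shown to be invalid.* That needs a normal or near-residual multiplier and a zero-variance fit accepted as a successful one. The SAP may rule out both. Nor do frequent collapse and serious harm coincide. Zero variance in about half of trials belongs to ICC 0.02–0.05, where the model loses only 1–2 points. At ICC 0.10–0.20, where coverage is poor, collapse falls to 37% and 25%.

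**Conclusion.** The point holds for what the protocol itself fixes. The ANCOVA interval omits the unit of randomisation and under-covers whenever the residual ICC is above zero: by about 2, 5, 11 and 20 percentage points at 0.02, 0.05, 0.10 and 0.20. The ICCs are assumptions. The coverage hardly changes between baseline correlations of 0.5 and 0.6. That the fixed-site fallback cannot estimate the arm effect is a matter of algebra and needs no assumption. Together these mean that failure of the mixed model would leave the ANCOVA interval as the only planned one.

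The mixed-model part is conditional: unless the SAP sets small-sample degrees of freedom and a rule for zero-variance fits, that model can also reduce to the ANCOVA interval.

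The consequence is confined to how the exploratory effect ranges are read. It merits correction but does not threaten the feasibility conclusions.

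**What to change.** In section 5 (Analysis), and in the SAP:

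1. Give the 95% CI from baseline-adjusted site means, compared between arms with t on 2 df, and name it as the interval to be read as the plausible range. Estimate the baseline slope from differences between children within sites, as in the check above. A slope fitted to the four site means would use one of the 2 df.
2. Use this analysis as the fallback in place of site as a fixed effect.
3. Present the ANCOVA as a point estimate, or keep its CI with a statement that it ignores clustering and is too narrow.
4. If the random-intercept model stays, state its degrees-of-freedom method and what is reported when the site variance is estimated as zero. Fixing its df at 2 is not an equivalent of item 1: that interval covered 99% or more at the ICCs tried, so it is not a 95% interval.

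The cost is wording only, with no new data. The downside is a much wider interval. With correlation 0.6, the median half-width is 0.95, 1.11, 1.27 and 1.56 SD at ICC 0.01, 0.05, 0.10 and 0.20, against 0.50–0.51 SD for the ANCOVA throughout. It will also be unstable, because its variance rests on 2 df. That width reflects what four sites can show.

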2. INTRODUCTION

Mental health problems are estimated to affect 10-20% of children and adolescents worldwide. Research shows that the prevalence of depression rises sharply after puberty and that over half of depressed adolescents have a recurrent episode within five years.

Mental health literacy can be defined as knowledge and beliefs about mental disorders which help people to prevent, recognise and manage problems. We know that low levels of mental health literacy significantly increase the risk of adolescents developing moderate to severe depression and that improving mental health literacy may be a useful way to reduce the future burden of depression amongst young people.

We have co-adapted with young people, parents, professionals and other stakeholders an existing interactive digital application, originally developed in Indonesia with MRC funding (IMPeTUs MR/R012741/1), to improve mental health literacy and self-management skills, for use in the UK with young people aged 12-14. We have also co-designed an additional third book designed specifically for young people in the UK.

The IMPeTUs intervention includes an immersive story line digital game in which young people play as two characters facing mental health challenges. Their decisions affect the direction of the game and eventual outcomes. This application will allow for UK specific intervention content to be developed and for associated materials to be co-produced with young people, parents, professionals and other stakeholders.

In the current study, we will test whether it is feasible to deliver and evaluate our intervention in education and community settings in the UK. We will randomly allocate 20 young people to receive our intervention and 20 to not receive it and then follow them up 3-months later. We will explore how many young people want to take part in our study (recruitment and retention), how much they use our intervention and what sort of follow-up data they are willing to provide. We will speak to facilitators (n=4-6), young people (n=10) and professionals (n=6-10) about their experiences of receiving and delivering our intervention and parents/guardians (n=6-10) about their their child's experiences with the intervention. We will use these findings to collaboratively design a larger study to explore the costs and impacts of our intervention.

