Comparator: Our comparator is assessment only. We will ascertain the range and variability in usual care. The frequency, amount and type of health services accessed by intervention and control arm participants will also be recorded. The control group will be offered access to the intervention at study end.

Feasibility outcomes: The primary outcomes are feasibility outcomes. We will assess CYP recruitment and retention rates, intervention uptake and engagement rates, and the variability and potential floor/ceiling effects in our proposed patient outcome measures. CYP outcomes will be measured as baseline (prior to randomisation), post-intervention (or at approximately 6 weeks post-randomisation for control group participants) and 3-month follow-up.

Clinical outcomes: The primary clinical outcome measure will be a version of the mental health literacy scale, the Knowledge and Attitudes to Mental Health Scale (KAMHS). Additional measures will include the short version of the Mood and Feeling Questionnaire (MFQ), the World Health Organisation Five Well-Being Index (WHO-5), the Revised Children's Anxiety and Depression Scale (RCADS), the Family Cohesion and Satisfaction with Communication subscales of the Family Adaptability and Cohesion Evaluation Scale (FACESIV), and the SF-36

Version: 2 Date: 11/7/2022 UREC ID: 2022-14361-24300

quality of life questionnaire. We will assess the feasibility of these different outcome measures as part of our feasibility trial.

At baseline, CYP demographics and psychiatric history will be recorded.

Analysis: As this is a feasibility trial, analysis will be mostly descriptive.

We will identify the number of study referrals, consents to research contact, and calculate cumulative and monthly recruitment rates. We will examine referral and recruitment rates between different sites (e.g. education and community settings) and recruitment routes (e.g. professional or self-referral).

The proportions of target sample size achieved, of participants who start and engage in the intervention, and the proportion retained in the study and providing outcome data will be calculated. Descriptive statistics will assess the completeness and variability of participant and cost outcome measures at each point.

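### The pre-set retention criterion covers the intervention arm only, so control-arm loss of any size cannot change a red/amber/green score

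*Protocol*

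**What the plan says.** Section 5 of the protocol lists three progression criteria: recruitment, retention and uptake. The second is headed "Progression criterion: Retention in intervention arm" and defined as follows: "Participants will be considered retained in the intervention arm if they are available for assessment at 3 month follow-up". All three bands carry the same restriction. The top band reads "Green: Retain > 80% of participants in the intervention arm at 3-month follow-up"; the red band (below 60%) and the amber band (60–80%) are likewise confined to that arm.

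The design has two arms of equal size: "We will randomly allocate 20 young people to receive our intervention and 20 to not receive it and then follow them up 3-months later" (section 2). Of the control condition, section 5 says "Our comparator is assessment only". Control participants are measured at baseline, at about six weeks after randomisation and at three months, and are offered the intervention when the study ends.

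The matching objective in section 4 is not limited to one arm. It speaks of "quantifying participant recruitment, retention and 3-month follow up rates" as the means of judging whether a cluster-randomised controlled trial is feasible. Under feasibility outcomes, section 5 likewise lists retention of the young people in general. Under analysis, it plans to calculate the proportion who stay in the study and supply outcome data, with no cut-off attached.

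**The concern.** A definitive controlled trial needs outcome data from both arms. The decision rule written here looks at one of them. If follow-up held up in the intervention sites and failed in the control sites, the retention criterion would give the same colour as if both had held up. The team would then have to decide, after seeing the data, how much control loss is tolerable. Pre-set progression criteria exist to avoid that kind of judgement. This is not a detail that a protocol may leave to the statistical analysis plan, because the protocol itself fixes the rule and its scope.

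**Working it through.** The 60% and 80% cut-offs are chosen, not derived, so the plan has no figure to reproduce. The check is what the rule as written does with possible results.

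**Inputs.** 20 participants per arm (section 2); two clusters of ten per arm (sections 4 and 5); bands of below 60%, 60–80% and above 80% (section 5). The documents give no expected retention rate, so every true rate below is an assumption.

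**Step 1: bands as counts out of 20.**
- Red: below 0.60 × 20 = 12, so 11 or fewer.
- Amber: 12 to 16.
- Green: above 0.80 × 20 = 16, so 17 or more.

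**Step 2: can another criterion register control loss?**
- Recruitment: a cluster is allocated only once its ten participants have been recruited, so this score is settled before any control follow-up.
- Uptake: concerns use of the intervention.
- Retention: intervention arm only.

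Nothing that happens in the control arm after allocation can change a colour.

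**Step 3: the rule applied to example results.**

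| Intervention | Control | Overall | Difference (points) | Score as written | Control on the same bands |
|---|---|---|---|---|---|
| 18/20 = 90% | 11/20 = 55% | 29/40 = 72.5% | 35 | green | red |
| 18/20 = 90% | 8/20 = 40% | 26/40 = 65% | 50 | green | red |
| 17/20 = 85% | 0/20 = 0% | 17/40 = 42.5% | 85 | green | red |

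Since a control arm is two sites of ten, one site that stops collecting data leaves at most 10/20 = 50%, which is red on these bands, and the score does not move.

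**Step 4: how often this could happen.** Exact binomial with n = 20 per arm, arms independent, clustering ignored. With true intervention retention of 90%, P(green as written) = P(X ≥ 17) = 0.867, whatever the control rate. The chance of green while control has 11 or fewer retained is 0.867 × P(control ≤ 11):
- control 40%: 0.867 × 0.9435 = 0.82
- control 50%: 0.867 × 0.7483 = 0.65
- control 60%: 0.867 × 0.4044 = 0.35
- control 70%: 0.867 × 0.1133 = 0.10

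**Step 5: the same cut-off in each arm.** P(green) = P(intervention ≥ 17) × P(control ≥ 17).
- 90% and 50%: 0.867 × 0.00129 = 0.001
- 90% and 70%: 0.867 × 0.10709 = 0.093
- 90% in both: 0.867 × 0.867 = 0.752
- 85% in both: 0.6477 × 0.6477 = 0.42, against 0.65 as written

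**Step 6: the cut-off applied to all 40.** Green needs more than 32, so at least 33. P(green) is 0.958 if both arms retain 90%, and 0.039 at 90% and 50%. Because the intervention arm can supply at most 20, a pooled green needs at least 33 − 20 = 13 controls (65%). Pooling therefore rules out green with a red control arm, but not green with an amber one.

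**The case against.** The strongest reply is that control loss would not be hidden. Section 5 plans to report the proportion retained and providing data, retention is a feasibility outcome for all the young people, and these results would be to hand when the definitive protocol is written. That stands, and it limits the harm: the objective of quantifying retention is still met. It does not supply a threshold, which is the gap.

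A second reply is that the proposed rule has its own cost. With two sites per arm, one disengaged site can set an arm's colour, and a gap between arms cannot be separated from a difference between sites. This also stands. It argues for reading an arm's colour alongside the site-level counts, not for leaving one arm out.

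Four stronger readings are tempting, and the documents do not support them:

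- *That controls are the arm most likely to drop out.* Nothing in the protocol says so. Controls are promised the intervention at study end, site staff issue the questionnaires, and the intervention arm carries the added load of at least 5–6 hours of participation. Which arm would lose more is unknown.
- *That unequal loss would bias the effect estimate.* Bias depends on how missingness relates to outcome. Unequal loss need not bias, and equal loss can.
- *That a definitive trial would be declared feasible despite losing half its controls.* There are three criteria, and the protocol states no rule that green on one of them, or on all, means proceeding.
- *That retention should require a completed primary clinical questionnaire.* Completion rates and the acceptability of the measures are assessed separately (sections 4 and 5). Merging them with retention would score an unsuitable questionnaire as failed follow-up.

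**Conclusion.** The point holds in a limited form. The retention criterion is fixed for the intervention arm alone, and no progression criterion responds to control-arm loss, although the trial is meant to inform a controlled comparison. This follows from the wording and rests on no assumed rate: on 20 per arm, any control count from 0 to 20 leaves the score unchanged. The probabilities illustrate scale only. They rest on assumed true rates and independent participants; clustering within two sites per arm would make the actual results more variable. The defect lies in one decision rule. It does not affect the data collected or the planned descriptive reporting, and it is worth correcting before the progression decision is taken.

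**What to change.** Retitle the criterion so that it covers retention in both arms, and define a participant in either arm as retained on the existing basis of availability at the 3-month assessment. Apply the 60% and 80% bands to each arm, let the worse arm set the colour, and report both arms' rates with the counts by site.

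The change is one of wording in the protocol, carried through to the statistical analysis plan. No new data are needed, since both arms are already assessed at three months. The price is that a well-run study reaches green less often: 0.75 instead of 0.87 at an assumed 90% in both arms, and 0.42 instead of 0.65 at an assumed 85%. If the team finds that too strict, a band on overall retention with a stated limit on the difference between arms is a workable alternative, and the protocol should say which was chosen.
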